## **6.3 Administration of Study Therapies**

The SSB intervention will be delivered in 5-1 ½ hour group sessions, on a twice-weekly basis, over a consecutive 3-week period. The HE intervention will be delivered in 1 hour group session.

### **6.3.1 Randomization**

The randomization will be within strata (CTP site). According to CTN coding, each site is a separate program or location. Separate block randomization schedules will be

developed for each CTP. This randomization scheme was chosen over individual randomization in order to hold the waiting time to group intervention to 4 weeks post baseline assessment. Under an individual randomization plan, excessive waiting periods might be necessary in order to accumulate enough subjects to conduct an intervention group. It should be noted that this randomization scheme poses the potential problem of imbalance between intervention conditions – in the event that a CTN sample (N = 40) is fulfilled by 5 cohorts of 8 subjects.

In each participating CTP clinic site, we will initially use block randomization to randomly assign our target (N=40) subjects to our intervention conditions in 6 cohorts. After baseline assessment, subjects will be placed into an open cohort awaiting randomization to one of the two intervention conditions. Randomization will be carried out either: when a cohort of 8 women has been recruited; or 4 weeks has passed since the first subject was placed in the cohort, whichever comes first. In the event that 3 participants have not been recruited in four weeks, the window will stay open until at least 3 participants have been recruited. Once closed, the cohort will be randomly assigned to one of the two intervention conditions – either the one receiving SSB intervention or the other receiving HE. If recruitment is rapid, a site may exceed the target of N=40 in 6 cohorts, up to approximately 48 subjects. If recruitment is slow, and <40 subjects have been randomized, we will initiate a second block randomization. If < 29 subjects (or an average of <5 subjects/group) have been recruited, a block randomization schedule for 4 more cohorts will be used. If 29 – 34 subjects have been recruited in the initial 6 cohorts, a block randomization schedule for 2 more cohorts will be used. If 35 – 39 subjects have been recruited in the initial 6 cohorts, 1 additional cohort will be randomly assigned.

Randomization will be managed through an outside independent randomization service provided by the Perry Point Cooperative Studies Coordinating Center (PPCSPCC). The PPCSPCC has designed and developed a centralized, automated telephone system to randomize subjects into clinical trials. Study sites access the system using a pre-specified phone number and respond to a series of prompts regarding the subjects' eligibility. After the system verifies subject eligibility, it assigns each subject a treatment assignment. Randomization can be done 24 hours a day, 7 days a week. Following each randomization, a fax notification is automatically sent to the site and others as needed. The system has also been programmed to send summary reports on a weekly basis.

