**TABLE 1: STUDY FLOW CHART**

Protocol Number 0019						
Study Activity	Visit 0	Visit 1	TX Session 1-5 a	Visit 2	Visit 3	Visit 4
	Day #	Day #	Day #			
Consent for screening assessment	1					
Screening assessment	1					
Obtain written informed consent	1					
Conduct baseline assessment		1-30				
Randomization of cohort			When 3 participants (but no more than 8) are in the cohort			
Attend intervention session(s)			Start approx day 8-36, attend over 1 or 3 weeks			
Conduct post intervention assessment				21 days after 1 st treatment session		
Conduct 3 mo. Follow up assessment					15 weeks after 1 st treatment session	
Conduct 6 mo. Follow up assessment						27 weeks after 1 st treatment session

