### **11.2 Sample Size and Statistical Power**

The sample size is determined to ensure sufficient power (at least 80%) of a significance test (with level of significance  $\alpha=0.05$ ) to detect a clinically meaningful intervention effect with respect to the primary outcome measure (number of unprotected penetrative sex occasions).

The study design is a stratified cluster randomization trial (Donner and Klar, 2000). The intervention groups constitute the clusters. Each intervention group will consist of approximately 3 to 8 women depending on the number of eligible subjects recruited in the fixed time interval of 4 weeks. The strata are the 12 CTP sites – in which 40 participants per stratum will be enrolled. Thus, within each stratum, 5 to 10 clusters will be randomized in a balanced fashion to the two interventions. Below is presented the power of the test for comparison of the two interventions subject to these design and recruitment restrictions. Tables 1 and 2 were developed for different counts of CTPs (with the number of subjects per CTP fixed at 40). The two tables corresponding to 12 CTPs (and shown in the protocol) resulted in power values that were closest to our goals.

The power analysis for the stratified cluster randomization trial is based on a test statistic proposed by Liu & Liang (1997). The test statistic is based on generalized estimating equation (GEE). The power analysis takes into account the fact that data are correlated (repeated observations on a subject, the measurements of subjects belonging to the same intervention group (cluster) and from the same CTP (strata) and that the outcome follows a non-normal distribution.

The test statistic is actually a quasi-score statistic based on the generalized estimating equation. The asymptotic distributions of the test statistic under  $H_0$  and  $H_1$  are both known. In the analysis we assume the outcome (the number of unprotected sex occasions) follows a Poisson distribution with the marginal mean being a function of the intervention. In this case, under the null hypothesis the test statistic converges to Chi-square distribution with 1 degree of freedom. Under the  $H_1$ , the test statistic converges to non-central Chi-square distribution with 1 degree of freedom. After we specify the parameters in the linear predictor for the mean and in the covariance matrix of the outcome (that is, the working correlation matrix which does not have to be necessarily

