- 2) within therapeutic group (cluster) correlation:  $\rho_2 = 0.15, 0.1$
- 3) within site (strata) correlation:  $\rho_3 = 0.1, 0.05$

The variance parameters are determined by the means described above, since the outcomes are Poisson random variables. When specifying the variances, there are two choices:

- 1) just Poisson variance, and
- 2) extra variation due to the effect of cluster and strata, i.e. over-dispersion.

Suppose that conditional on cluster and strata the variance of the outcome is a Poisson variance, for example, the variance of the outcome (X) in the control intervention with mean 17 is  $\text{Var}(X|\text{cluster, strata})=17$ . Then the marginal variance of the outcome is over-dispersed to  $\text{Var}(X)=17/(1-\rho_2-\rho_3)$ . For the experimental intervention group with mean 15 the over-dispersion is  $15/(1-\rho_2-\rho_3)$ . Presented are results for Poisson and for over-dispersed Poisson variation.

As explained above, the intervention groups' size will vary between 3 and 8; and therefore the number of clusters (intervention groups) within strata (CTP) will be between 10 and 5. From a statistical perspective it is advantageous to have small clusters (intervention groups of size 4) and many clusters per strata (here 10 clusters for a total of 40 subjects per strata (CTP)); such design will have higher power than a design where the clusters will be large but the number of clusters per strata will be small as it is when there are 8 subjects per intervention group for a total of 5 intervention groups per CTP. We present the power computations for these two extreme cases.

The tables below give the power of the test as a function of rho1, rho2, rho3 and mean number of unprotected penetrative sex occasions in the two intervention groups.

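### The range of 5 to 10 cohorts per site does not follow from group sizes of 3 to 8, the cohort rules can leave a slow site at 30 women instead of 40, and they conflict at 29 women

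*Protocol*

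**What the plan says.** Section 11.2 sets the size per site: "The strata are the 12 CTP sites – in which 40 participants per stratum will be enrolled". It then says that "within each stratum, 5 to 10 clusters will be randomized in a balanced fashion to the two interventions". Further on it gives the reason for that range. Of the intervention groups it says that their "size will vary between 3 and 8; and therefore the number of clusters (intervention groups) within strata (CTP) will be between 10 and 5". The next sentence uses a different lower size: "it is advantageous to have small clusters (intervention groups of size 4) and many clusters per strata (here 10 clusters for a total of 40" women per site). Ten groups of 4 and five groups of 8 are presented as the two extremes, and they are the only designs in the section's power Tables 1 and 2.

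Section 6.3.1 gives the operating rule. A site starts with six cohorts. A cohort closes at 8 women or after four weeks, and stays open past four weeks only until it holds 3. If six cohorts leave the site short of 40, a second block follows: "If < 29 subjects (or an average of <5 subjects/group) have been recruited, a block randomization schedule for 4 more cohorts will be used". A site with 29 to 34 women gets two more cohorts, and a site with 35 to 39 gets one. Nothing is said about a site that is still short after the second block.

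**The concern.** Three things do not fit together.

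- The upper end of the cohort range is presented as following from a minimum group size of 3, but it is the figure for size 4. The two power tables therefore do not cover the smallest groups that the rules permit.
- The longest path described in 6.3.1 has ten cohorts. With cohorts of 3, a site can follow every stated rule and finish well below the 40 on which the power section rests.
- The text gives two different instructions for a site with 29 women after six cohorts.

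At stake are the accuracy of the stated size and power, and a randomization schedule that can be loaded into the central automated system without someone having to interpret it.

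**Working it through.** **Cohort range.** The inputs are 40 women per site and sizes 3 to 8 (Section 11.2).

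- Size 8: 40/8 = 5, as stated.
- Size 4: 40/4 = 10, as stated, but for size 4.
- Size 3: 40/3 = 13.3, so 13 to 14 groups and not 10.

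**Women at the end of the schedule.** The inputs are six initial cohorts, the three branches and the minimum cohort of 3 (Section 6.3.1). The fewest women is the number after six cohorts plus 3 for each added cohort.

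| Women after six cohorts | Added cohorts | Fewest women at the end |
|---|---|---|
| 18 (six cohorts of 3) | 4 | 18 + 12 = 30 |
| 28 | 4 | 28 + 12 = 40 |
| 29 | 2 | 29 + 6 = 35 |
| 34 | 2 | 34 + 6 = 40 |
| 35 | 1 | 35 + 3 = 38 |

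From 18 women, the four added cohorts would have to average (40 − 18)/4 = 5.5 to reach 40. At an unchanged pace, 18 women become 18 × 10/6 = 30, 20 become 33, 23 become 38 and 24 become 40.

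**The branch rule at 29.** 29/6 = 4.83, which is below 5, so the parenthesis calls for four more cohorts. The 29–34 band calls for two. At 30 the average is exactly 5, and 30 × 8/6 = 40, so a cut at 30 agrees with the average.

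**Power.** The inputs from Section 11.2 are 12 sites, two follow-up measures, Poisson variances equal to the means, and the correlations rho1 (within subject), rho2 (within group) and rho3 (within site). The test is two-sided at 0.05 (Section 11.5.1). The protocol uses a quasi-score test. A normal approximation for the same design, with m women per group and k groups per arm and site, is:

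- B = (1 + rho1)/(2m) + rho2 (m − 1)/m − rho3
- Var = B × (mean SSB/k SSB + mean HE/k HE)/12
- Power = Φ(difference/√Var − 1.96)

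The protocol's own figures come first, for 17 versus 16 at 0.40/0.10/0.05 without over-dispersion:

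- Ten groups of 4: B = 0.175 + 0.075 − 0.05 = 0.200; Var = 0.200 × 33/5/12 = 0.110; power = Φ(3.015 − 1.96) = 0.854. Power Table 1 gives 0.85.
- Five groups of 8, two SSB and three HE: B = 0.0875 + 0.0875 − 0.05 = 0.125; Var = 0.125 × (16/2 + 17/3)/12 = 0.142; power = 0.755. Power Table 2 gives 0.75.

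The formula matches every cell without over-dispersion in both tables to within 0.01.

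Now ten groups of 3 at every site, for 17 versus 16:

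- 0.40/0.10/0.05: B = 0.2333 + 0.0667 − 0.05 = 0.250; Var = 0.250 × 33/5/12 = 0.1375; power = Φ(2.697 − 1.96) = 0.77. The tables give 0.85 and 0.75.
- 0.40/0.10/0.10: B = 0.200; Var = 0.110; power = 0.85. The tables give 0.94 and 0.93.

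For 17 versus 15.5, the lowest value over all correlation sets is at 0.80/0.15/0.05 with over-dispersion, where the inflation is 1/(1 − 0.15 − 0.05) = 1.25. There B = 0.350, Var = 1.25 × 0.350 × 32.5/5/12 = 0.237, and power = Φ(3.081 − 1.96) = 0.87.

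For contrast, fourteen groups of 3 (42 women, seven groups per arm) at 0.40/0.10/0.05 give 0.89 for 17 versus 16. Any loss therefore comes from ending at 30 women and not from small groups.

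**The case against.** The case on the other side is substantial.

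- **No cap is written.** Section 6.3.1 describes topping up towards a target, and the ten-cohort ceiling is inferred from the absence of a third block. If ten is the maximum, 5 to 10 is the right range for the schedule and only its derivation is wrong. If it is not, the shortfall to 30 disappears. This stands, and it is why the text must say which applies.
- **Forty is approximate elsewhere.** The synopsis says approximately 480, Section 5.1 about 40 per site, Section 6.3.1 calls 40 a target, and Section 11.4 speaks of an average of 40. Fast sites may reach about 48 and offset slow ones. A reader might infer that the trial is heading for 12 × 30 = 360 women. The documents do not support that: it needs every cohort at every site to close at the minimum.
- **Power for the main differences survives.** Section 11.2 rests its claim on 17 versus 15 or 15.5 and already calls power for 17 versus 16 somewhat limited. At 0.40/0.10/0.05 the worst case of 0.77 is even above the 0.75 in power Table 2. It falls materially below both tables only when rho2 and rho3 are both 0.10.
- **The bands at 29 can be operated.** The three numeric bands do not overlap, and only the parenthesis misfits, at one value. That makes the error small, but it is still two instructions for one site.

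A reader might also take the study flow chart's entry, "When 3 participants (but no more than 8) are in the cohort", to mean that randomization happens as soon as 3 women are present. It is better read as shorthand for the size limits. Sections 4.0 and 6.3.1 give the full rule consistently, so this is not a contradiction.

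**Conclusion.** The point holds at moderate to low weight. The upper end of the cohort range is miscalculated for size 3, ten groups of 4 is not an extreme of what the rules allow, and the branch rule contradicts itself at 29 women. A slow site can end at 30 women if no block follows the tenth cohort, which the protocol leaves open.

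The power figures of 0.77 and 0.85 assume ten groups of 3 at all 12 sites and the protocol's own variance model without over-dispersion. They bound the effect and do not forecast it. The 80% goal for 17 versus 15.5 is met even then. What weakens is the added statement in Section 11.2 that groups of 4 can give enough power for a difference of one occasion. In power Table 1, 7 of 12 such cells without over-dispersion reach 0.80. With ten groups of 3, one does clearly (0.85) and two sit at 0.797.

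**What to change.** 1. In Section 6.3.1, set the first cut to fewer than 30 women (average below 5) and start the next band at 30 to 34.
2. In both places in Section 11.2, say that 5 to 10 groups applies to sizes 4 to 8, and that size 3 needs 13 to 14 groups for 40 women.
3. Settle what happens after the tenth cohort, in one of two ways:
   - State that ten cohorts is the maximum, give the possible size as about 30 to 48 women per site (48 is the protocol's own figure for a fast site), and add the case of ten groups of 3 to the power section.
   - State that a further balanced block follows when ten cohorts leave a site below 40.

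Steps 1 and 2 cost only wording and a change to the randomization schedule. The first option in step 3 costs a less favourable stated size and power. The second costs time at slow sites: fourteen cohorts of 3, each open for at least four weeks, take at least 14 × 4 = 56 weeks if run one after another, against 8 to 12 months of recruitment in Section 5.2 and about 6 months in Section 11.4. Any further block should not become an open-ended series of blocks of two, because every second assignment would then be predictable, while Section 6.3.2 wants assessors kept unaware of the balancing plan.

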## 5.0 Study Population

### 5.1 Number of Sites and Subjects

The study will be carried out in approximately 6 MMTPs and 6 ODFs who can each provide about 40 sexually active women, who have had unprotected penetrative intercourse with a male within the last 6 months. As much as possible, the same sites will also participate in the companion protocol for men. Final site selection will occur only after the protocol has been certified, and will observe CTN/CTP procedures for protocol selection. Site selection will be guided by the goal of obtaining diversity – in terms of ethnicity, region and primary drug of abuse.

Subjects will be approximately 480 women (i.e. 240 women/intervention condition) in MMTP (N = 240) or outpatient drug treatment (N=240) who fulfill criteria for being at heightened risk for HIV/STD heterosexual transmission. This will include women of all racial and ethnic groups. Inclusion of both MMTP and other outpatient drug treatment will provide the opportunity to reach two important subgroups of female drug users: those whose primary substance of abuse is heroin (MMTP); and those whose primary substance of abuse is likely to be cocaine or other stimulants (outpatient drug treatment). In as much as women often face a distinct set of powerful obstacles to safer sex - especially associated with gender role pressures (for interpersonal and sexual submissiveness), gender role responsibilities (for motherhood and childrearing) and vulnerability to domestic violence, - restriction to women only is an essential feature of the skills building intervention. It is under these conditions that [name] ([name] and Schilling, 1992) and Schilling (Schilling et al., 1991) proved its efficacy. As such, it has the disadvantage of excluding men. The companion protocol for men will offer a comparable trial of a gender-specific intervention to men in the same settings.

Subjects will be recruited through a number of vehicles, as appropriate at each site. Recruitment may include posters and fliers conspicuously placed in CTP waiting rooms; announcements about the study to clinic patients, and directly through a participant's individual counselor. These will invite all women to see the research assistant situated in the CTP, or to call the study phone or voicemail.

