### **6.3.2 Blinding**

Both therapist and subject blinding to intervention condition is not feasible. An effort will be made to keep research assistants conducting assessments blind to intervention condition and the plan for balancing number of cohorts assigned to each intervention condition within each CTP site.

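### Section 6.3.1 prints the per-site cohort block lengths that Section 6.3.2 wants assessors not to know, so the arm of some still-open cohorts could be deduced

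*Protocol*

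**What the plan says.** Randomization is stratified by site, and whole cohorts of about 3 to 8 women are assigned together. Section 6.3.1 says the site will "randomly assign our target (N=40) subjects to our intervention conditions in 6 cohorts". If these six yield too few women, the rule continues by recruitment count:

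- fewer than 29 women: "a block randomization schedule for 4 more cohorts will be used";
- 29 to 34 women: "a block randomization schedule for 2 more cohorts will be used";
- 35 to 39 women: "1 additional cohort will be randomly assigned".

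Section 11.2 adds that within each site "5 to 10 clusters will be randomized in a balanced fashion to the two interventions".

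Section 6.3.2 accepts that therapists and participants cannot be blinded. For research assistants who conduct assessments, it says an effort will be made to keep them "blind to intervention condition and the plan for balancing number of cohorts assigned to each intervention condition within each CTP site".

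On recruitment, Section 5.1 says of the posters, announcements and counselor contacts: "These will invite all women to see the research assistant situated in the CTP". Section 5.4 has the research assistant or site coordinator introduce the study. After baseline, a woman joins an open cohort, which is assigned only once it closes, through an independent telephone service that faxes the result to the site (Section 6.3.1).

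**The concern.** The information that Section 6.3.2 wants withheld is set out in Section 6.3.1 of the same protocol, which Section 13.0 allows to be disclosed to staff as needed to run the study. Earlier arms are not secret at a site: one condition is a single session, the other is five, neither is blinded, and each assignment is faxed. With the block length and the earlier arms in hand, the last assignment in a balanced block follows by subtraction.

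Because a cohort fills before it is assigned, this could matter even though the call comes after closure. If the arm is already known, a woman's entry can be moved to this cohort or the next; Table 1 gives baseline a window of days 1 to 30. Section 4.0 also replaces women who leave before they are told their assignment, on the assumption that leaving is unrelated to it. For a foreseeable cohort that assumption is weaker.

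**Working it through.** **Inputs.** Block lengths of 6, 4 and 2, and the single top-up cohort, are from Section 6.3.1. The splits 3:3, 2:2 and 1:1 are an assumption, inferred from the words block and balanced in Sections 6.3.1 and 11.2; the ratios are not printed. The observer is assumed to know the printed length and every earlier arm at the site.

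**Method.** Take all balanced sequences of a block as equally likely. A position is certain when one arm has already used up its share.

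*Block of 6.* There are C(6,3) = 20 sequences.

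- Cohorts 1 to 3: never certain.
- Cohort 4: certain if the first three share one arm, 2/20 = 0.10.
- Cohort 5: certain if the last two positions share one arm, 2 × C(4,1) = 8, and 8/20 = 0.40.
- Cohort 6: always certain, 1.00.
- Expected number: 0.10 + 0.40 + 1.00 = 1.5 of 6 (25%).

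*Block of 4.* There are C(4,2) = 6 sequences. Cohort 3 is certain in 2/6 = 0.33 and cohort 4 always: 1.33 of 4 (33%).

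*Block of 2.* The second cohort is always certain: 1 of 2 (50%).

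*Single top-up cohort.* Never certain.

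| Course at a site | Certain cohorts | Share |
|---|---|---|
| 6 only | 1.5 of 6 | 25% |
| 6 then 4 | 1.5 + 1.33 = 2.83 of 10 | 28% |
| 6 then 2 | 1.5 + 1 = 2.5 of 8 | 31% |
| 6 then 1 | 1.5 of 7 | 21% |

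Section 6.3.1 also mentions a site that fills its 40 places with five cohorts of eight. There the sixth, always certain position is never reached, and the figure falls to 0.10 + 0.40 = 0.5 of 5 (10%).

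**Power.** The protocol gives no figure for predictability. Its power figures serve to check that withholding the lengths costs nothing. A within-site comparison of cluster means has variance V × [(1+ρ1)/(2m) + (m−1)ρ2/m − ρ3] × (1/k_SSB + 1/k_HE)/12. For the first row of Table 1 in Section 11.2 (17 against 16, no over-dispersion): V = 16.5, m = 4, k = 5 per arm, and the bracket is 0.175 + 0.075 − 0.05 = 0.20. The variance is 16.5 × 0.20 × 0.4/12 = 0.11, so SE = 0.332 and power = Φ(1/0.332 − 1.96) = 0.85, as stated. Only the number and size of groups per arm enter. Who knows the block length does not.

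**The case against.** Printing a plan is not the same as showing it to everyone. Section 13.0 limits disclosure to what staff need, Section 14.4 has the site principal investigator sign, and nothing says that research assistants read Section 6.3.1 or receive the fax. Section 6.3.2 promises only an effort, and only for those who assess. This stands: a reader might infer that recruiters can in fact foresee the arm, and the protocol does not establish that. It does not answer the point entirely, because the protocol does not separate assessing from recruiting research assistants. Counselors, who may also recruit (Section 5.1) and from whom the therapists are drawn (Section 6.2), are not covered by the blinding aim.

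A reader might also infer that late cohorts are generally predictable. In the first block only the sixth always is.

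A third tempting reading is that guessing the arm used less often so far is right 68%, 71% and 75% of the time in blocks of 6, 4 and 2, against 50%, and that hiding the lengths would restore the 50%. It would not. That guess needs only past arms and an expectation of balance, so a hidden block of 6 still gives 68%. Splitting six cohorts into 4 and 2 gives (2.833 + 1.5)/6 = 72%. The 50% belongs to independent assignment of each cohort, which is not proposed here. These rates therefore do not measure what the fix achieves.

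Finally, there are safeguards: closure by rule, central assignment after closure, structured eligibility checks (Section 8.2.1) and adjustment for the baseline outcome and monogamy status (Section 11.6.1). They narrow the route to bias, but closure and central assignment do not prevent deduction from a known length, and the adjustment covers only those two variables.

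**Conclusion.** The point holds as a minor one. Section 6.3.1 makes available what Section 6.3.2 sets out to withhold. The certain shares are 1.5 of 6, 1.33 of 4 and 1 of 2. They are upper bounds: they assume that each printed count is one evenly split block, and an observer who has both the lengths and the full site history. The first cohort of a block and the single top-up cohort are never foreseeable. Blocks of 4 and 2 arise only where six cohorts yield fewer than 35 women.

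The protocol does not show that anyone would act on such knowledge, and the size of any selection bias cannot be derived from it. The finding is an avoidable weakness in concealment, not evidence that the comparison is biased.

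**What to change.** Take the block lengths and the recruitment thresholds for further cohorts out of the site-facing text of Section 6.3.1. Put them in a restricted document held by the central randomization service already named there. Have that service tell a site only whether to open another cohort. Keep the balanced scheme itself unchanged.

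This removes certainty that rests on the printed lengths. It does not remove the partial predictability that comes from expecting balance within a site, and the text should not claim that it does.

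The cost is a change of wording and one restricted file. Power is unaffected, but sites can no longer foresee their exact number of groups, which makes staffing somewhat harder to plan. Varying the block lengths at the centre is optional: with about six cohorts per site, it could leave a site unbalanced if recruitment stops in mid-block, and Sections 11.2 and 11.5.4 rely on comparing the two conditions within each site.
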